2.3 Duration of follow-up

It was planned that each patient would be followed up for the duration of the interval between usual care clinic follow-up visits (expected to be 8-24 weeks). Because of the Covid19 pandemic starting March 2020, end-of-study clinic visits for two patients were not conducted and end-of follow-up for these patients was arbitrarily defined as 30 April 2020. The duration of follow-up varied for each patient.

3. Study design

3.1 Summary of design, including control

Open-label, single-arm observational study of patients treated in a usual care environment.

There was no control group.

3.2 Study population

Adult patients with a diagnosis of idiopathic pulmonary fibrosis [2].

3.3 Observational intervention

The observational intervention was an electronic health diary (pMp) supplied with a Bluetooth-connected home spirometer (MIR Sprobank Smart).

pMp+home spirometry was developed specifically for patients with IPF. pMp is an electronic application downloaded to the patient's mobile phone or tablet device. It is designed to allow the patient to report various parameters relevant to IPF and record these on a regular basis. The information recorded by the patient is stored in a secure cloud and is available to the patient through their phone or mobile device at all times. No personal health data are stored on the phone or mobile device itself. Patients were asked to report measurements on pMp each day e.g. Forced Vital Capacity (FVC; (one reading once/day), dyspnoea, activity (steps/day), distance walked per day and compliance with IPF medication. Patients were prompted to report the impact of IPF on daily life using a Patient Reported Outcome Measure (PROM) developed specifically for IPF [3]) once every week.

3.4 Concomitant therapy, restrictions and rescue treatment

There were no restrictions on concomitant treatment. All concomitant treatments as prescribed by the patient's healthcare professionals were allowed. Patients continued to take all medicines as prescribed by their healthcare professionals.

There were no restrictions on diet or life-style. Patients continued to follow all instructions on diet, exercise and lifestyle as directed by their healthcare professionals.

4. Variables for assessment

4.1 Efficacy variables

The objectives of this observational study were:

- to assess and characterise the longitudinal trends of patient-measured FVC and PROMs in a cohort of patients with IPF
- to determine the correlation (if any) between patient-measured FVC and PROMs with clinic-observed measurements
- to assess if longitudinal trends in patient-measured FVC outcomes are predictive of clinical health outcomes in IPF
- to assess the acceptability and utility of pMp

The primary endpoint was the longitudinal trend in patient-reported FVC. The correlation between patient-reported FVC and clinic-reported measures and outcomes were also assessed.

The primary endpoint variable was the daily patient-reported FVC.

The secondary endpoints included:

- the longitudinal trend in PROMs
- the correlation between PROMs and clinic-reported measures and outcomes.
- assessment if patient-measured FVC predicts clinical health outcomes
- the impact of active engagement and self-monitoring using pMp on the impact of IPF on daily life (PROM)
- the effect of pMp on medication compliance
- the acceptability and utility of pMp (from patient and healthcare professional perspective)

The secondary endpoint variables (reported by patients) were:

- maximum level of dyspnoea each day (ideally linked to description of activity causing maximum dyspnoea)
- activity (number of steps/day)
- distance walked per day
- compliance with medicines prescribed for treatment of IPF
- addition of any new prescribed medicines for treatment of IPF
- impact of their medical condition on their daily life (once/week; PROM)

Additional secondary endpoint variables which can be recorded by the patients (if measurement devices are available to the patient and it is practical for the patients to record these variables) include:

- duration of walking per day
- number of episodes of walking per day
- cough (worst severity each day)
- heart rate (if patient has access to wearable fitness device)
- blood pressure (if patient has access to measurement device)
- temperature (if patient has access to measurement device)
- body weight (once/week)
- oxygen saturation at rest (if patient has access to pulse oximetry device and wishes to record saturation)
- oxygen consumption (cylinders/month)

Patients assessed dyspnoea with the mMRC dyspnoea scale which may be a useful prognostic indicator in IPF [4].

The secondary endpoint variables (assessed and recorded by the clinic) are:

- FVC
- dyspnoea
- impact of the patient's medical condition on their daily life (using the same PROM questions used by the patient)
- health outcomes e.g.

- medication adherence
- change in IPF medication (dose change or new medicine prescribed)
- oxygen usage
- exacerbations of IPF
- hospitalisations due to IPF

The patient's opinion of the utility and acceptability of pMp as assessed by their response to questions:

- the instructions given in using pMp were clearly understandable (strongly agree/agree/disagree/strongly disagree)
- using pMp helped me to take the correct dose of my medicines for lung fibrosis every day (strongly agree/agree/disagree/strongly disagree) [only asked if patient is taking medication specifically prescribed for IPF]
- using pMp helped me to reach my personal exercise goal every day (strongly agree/agree/disagree/strongly disagree)
- using pMp helped me to walk further (or exercise more) compared with before (strongly agree/agree/disagree/strongly disagree)
- using pMp gave me more confidence/a greater sense of control in managing my lung health (strongly agree/agree/disagree/strongly disagree)
- I found it useful to be able to record the impact of lung fibrosis on my daily life (strongly agree/agree/disagree/strongly disagree)
- I liked using pMp (strongly agree/agree/disagree/strongly disagree)
- pMp was easy to use (strongly agree/agree/disagree/strongly disagree)
- the effect of using pMp on the impact of lung fibrosis on my well-being and daily life (positive, negative)
- I found it tiring or irritating to use pMp (strongly agree/agree/disagree/strongly disagree)
- I want to continue using pMp after the end of the study (yes, no)
- I would recommend other people with my condition to use pMp (yes/no)
- what other measurements, reminders or information would be useful to have on pMp? (Open text for participant to give opinion)
- describe the benefits and/or disadvantages of using pMp (Open text for participant to give opinion)

The secondary endpoint will also be assessed by the healthcare professional's response to the following questions:

- preference for using pMp versus not using it (yes, no preference, no)
- difficulty rating in using pMp (very easy, easy, difficult, very difficult)
- did using pMp help me to help the patient manage their IPF better? (yes, no)

- did using pMp help the patient to take their IPF medicines at the correct dose every day (yes, no) [only asked if patient is taking medication specifically prescribed for IPF]
- do I believe the patient should continue using pMp after the end of the study (yes, no)
- what other measurements, reminders or information would be useful to have on pMp? (Open text for healthcare professional to give opinion)
- describe the benefits and/or disadvantages of using pMp (Open text for healthcare professional to give opinion)

4.2 Safety

All observed adverse events were listed.

4.3 Other variables

Demographic data (date of birth, gender, ethnicity, height, weight, concomitant diagnoses, medication prescribed).

Engagement of patients with pMp was assessed by analysis of the numbers of patients who used pMp and the frequency of recording study measurements.

5. Statistical methods and determination of sample size

5.1 Statistical design and model

The study was an open-label, prospective, single-arm observational study of patients treated in a usual care environment.

There was no control group.

5.2 Null and alternative hypotheses

Not relevant.

5.3 Planned analysis

All data from the Treated data set were included in the analysis. The list of variables, data formats, data presentations, statistical comparisons and statistical tests used are shown in Appendix 1 (section 7).

Results were summarised for descriptive statistical display. No imputations of missing data were made.

The primary efficacy endpoints were assessed by analysis of changes in patientreported FVC, clinic-derived parameters and health outcomes over time.

Patient-reported FVC and other patient-reported measures were compared with the clinic-derived measures and health outcomes to determine if there were any correlations between them.

The secondary endpoints data were assessed by analysis of changes in the patient-reported health parameters, clinic-derived parameters and health outcomes over time.

Data on the level of engagement with pMp and the patient opinions were described and tabulated.

Patient-recorded FVC data were screened to detect outlier values (e.g. where a patient did not blow forcefully enough or may have coughed during the forced expiratory maneuver). The average patient-recorded FVC was tracked over time via the Exponentially Weighted Moving Average (EWMA) adjusted for irregular time indices [5,6]. Control limits were constructed via the EWMA variance, which accounted for the stochasticity around the mean, plus an adjustment 0.15*log(max(delta_t, 1)), where delta_t is the time since the last observation, for the purpose of modelling our uncertainty due to lack of engagement during periods where the patient was not inputting spirometry values. Any values outside these control limits were considered outliers. Scatter plots of patient-recorded FVC versus time were prepared for each patient.

Correlation between clinic-observed and patient-recorded FVC was assessed as follows. The means of the first seven days of patient-recorded FVC after baseline and of the last seven days of patient-recorded FVC before the end-of-study clinic visit were calculated. Outlier values were detected by inferring a rolling average of the patient-recorded data using the EWMA algorithm and removing values far away from this average, taking into account heightened uncertainty of the average during periods of poor engagement. Outlier values were excluded and the means of spirometry values within the first seven days after the baseline clinical FVC (mean baseline spirometry) and the last seven days before their end-of-study clinical FVC (mean endpoint spirometry) were calculated. Patients without a single spirometry value in either 7 day window were excluded.

For both baseline and end-of-study, the correlation between in-clinic FVC and patient-recorded FVC was calculated by randomly sampling from the data with replacement and calculating the usual Pearson correlation coefficient. This process was repeated 1000 times, giving an empirical distribution for correlation. This process is known as bootstrapping [7]. The mean of this distribution is the inferred correlation, and the standard error is the standard deviation of this distribution divided by the square root of 1000.

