	address, demonstrated
	understanding of use of
	patientMpower app and home
	spirometry, written informed consent

TEST PRODUCT	patientMpower app (via patient's
	smartphone or tablet device)
DURATION OF OBSERVATION	Sixteen (± eight) weeks
END OF STUDY DEFINITION	Sixteen (± eight) weeks
PRIMARY ENDPOINTS	Trend of patient-measured FVC over
	time.
	Degree of correlation between
	patient-measured FVC with clinic-
	observed measures.
SECONDARY ENDPOINTS	Trends of patient-reported
	outcomes over time.
	Degree of correlation between
	patient-reported outcomes with
	clinic-observed measures.
	Patient and healthcare professional
	perspectives on preference for and
	difficulty using the app and
	helpfulness in managing IPF.
	Impact of app on patient self-
	management of IPF and daily living.
INTERIM ANALYSIS	None planned
STATISTICAL METHODS	Descriptive statistics tables will be
	prepared

FLOW CHARTS

Flow chart 1: Patient recruitment process

Step	Day	Action
1	0 (Baseline)	At a usual care visit to study centre, research team discusses study with patient (face-to-face), confirms patient's understanding of the study processes and willingness to participate. Obtains written informed consent ^A . Study centre conducts usual clinical assessments. Study starts.
2	0 (Baseline)	Study centre advises patientMpower Ltd. of email address of patients who have given consent to participate.
3	0 -2	patientMpower sends information pack (electronic; includes instructions on installation of app) and home spirometer to patient ^B .
4	0 - 2	Patient starts to use patientMpower app and home spirometry as soon as possible after installation of app and pairing of spirometer.

^A Includes explicit consent by patient for patientMpower to know their identity and email address and collect, store and analyse data reported by the patient on the patientMpower app.

^B On request by the patient, patientMpower Ltd can contact patient to offer help with installation of patientMpower application and pairing of spirometer (so that application and spirometer are installed and operating correctly).

Flow chart 2 Assessments during observation period

	Baseline (clinic visit)	Install app & pair spirometer	*Daily (patient -reported)	16 (±8) weeks End study (clinic visit) ¹
	day 0	day 0-2	daily	week 16
				(approx.)
Informed consent	Х			
Start of study	Х			
Spirometry, assess	Х			Х
dyspnoea	N N			
Demographic data (include IPF history & medicines	X			
history ³)	X			
Patient training & encouragement	~			

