6.2.2 Baseline clinic visit

The study procedures and assessments during the observation period at each clinic visit are summarized in flow-chart 2 on page 7.

At a usual care visit to the study centre, the research team will discuss the study with the patient (face-to-face), confirm their understanding of the study processes and their willingness to participate.

Written informed consent will be obtained before any study-specific assessments and before installation of the patientMpower app.

The study starts at this visit.

The patient will be instructed in the correct use of the Spirobank Smart home spirometer and uploading of data to the patientMpower app. The patient's understanding of the patientMpower app, Spirobank Smart home spirometer and the study procedures should be checked before they leave the clinic.

Demographic data, medical history and concomitant therapy for IPF and other respiratory conditions will be recorded.

The following parameters will be assessed and recorded in the clinic records:

- spirometry (to include FVC)
- dyspnoea (e.g. UCSD Shortness of Breath Questionnaire or other measure usually used by the investigator sites) impact of IPF on daily life (using the same PROM as in the patientMpower app)

The study centre will advise patientMpower Ltd that the patient has consented to participate in the study and provide the patient's contact details.

patientMpower Ltd. will send the patient an information pack (via email) and a home spirometer (via regular mail or courier). The information pack will give instructions (including video clips) on how to install the patientMpower app onto your smartphone or tablet device and how to pair the spirometer with the app. During the installation, some information on the patient (e.g. date of birth and gender) will be recorded on the patientMpower app. If necessary, the patient may be loaned a tablet device (like an iPad) which will have the patientMpower app installed. If requested by the patient, patientMpower Ltd. will provide technical support to the patient in downloading the app and pairing with the spirometer.

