6.2.3 Treatment and observation period

Patients will be encouraged to record the parameters described in section 5.1.1.1 and 5.1.1.2 on a regular basis.

The following should be recorded by the patient each day:

- FVC (one spirometry manoeuvre each day ideally at approximately the same time each day but this is not essential)
- compliance with medication prescribed for IPF (if prescribed)
- any changes to medication taken for IPF
- activity (number of steps per day)
- distance walked per day
- maximum level of dyspnoea

Impact of IPF on daily life (PROM) should be recorded by the patients every week.

Patients will receive reminders (via the patientMpower app) at appropriate intervals to record study parameters.

Other parameters should be recorded by the patient (if suitable measurement devices are available to the patient and where practical for the patient) frequently. Examples include duration of walking, number of episodes of walking, cough, heart rate, blood pressure, temperature, body weight, oxygen saturation and oxygen usage (e.g. cylinders/month).

If requested by the patient, patientMpower Ltd will provide technical support on correct use of the app or spirometer at any time during the study.

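### The primary home-FVC trend has no familiarisation period and no analysis without the early readings, so initial inexperience could mask decline, mainly at short follow-up or in a start-to-end change

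*SAP*

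**What the plan says.** SAP 4.1 sets the target: "The primary endpoint was the longitudinal trend in patient-reported FVC". The variable is the daily home reading. On which readings count, SAP 5.3 says: "All data from the Treated data set were included in the analysis". The only filter described is an outlier screen based on an exponentially weighted moving average (EWMA). No reading is set aside because it falls early.

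Home recording begins at once. Protocol Flow chart 1, step 4, has: "Patient starts to use patientMpower app and home spirometry as soon as possible after installation of app and pairing of spirometer". Protocol 6.2.3 asks for "one spirometry manoeuvre each day ideally at approximately the same time each day but this is not essential". The patient's own spirometer is sent out after the baseline visit (Protocol 6.2.1 and 6.2.2).

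There is training. Protocol 6.2.2 states: "The patient will be instructed in the correct use of the Spirobank Smart home spirometer and uploading of data to the patientMpower app". It also asks staff to check understanding before the patient leaves, and Protocol 3.3.2 makes demonstrated understanding of correct spirometer use an inclusion criterion.

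Follow-up per patient is "expected to be 8-24 weeks" (SAP 2.3). SAP 5.3 does define a start window, "The means of the first seven days of patient-recorded FVC after baseline", but for the correlation with clinic FVC, not for the trend. SAP 5.3 and 7.1 place the detailed presentations and tests in an Appendix 1 that is not part of the text available.

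**The concern.** FVC depends on effort, and SAP 5.3 itself expects some blows to be too weak. A patient new to the device may read low for the first days and then settle. In a single-arm study nothing separates that rise from the course of disease. It acts against the progressive decline that Protocol 1.1 describes, so the cohort could look more stable than it is. Because follow-up varies threefold, the bias would also differ between patients. That matters for the secondary aim of relating home FVC to clinical outcomes. The outlier screen is aimed at isolated departures from a running average, and a gradual rise would tend to be followed by that average rather than flagged.

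**Working it through.** The plan gives no learning gain, no expected decline and no trend estimator, so there is no figure of its own to reproduce.

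**Inputs from the documents.** One reading per day (Protocol 6.2.3); 8, 16 and 24 weeks (SAP 2.3 and synopsis), so n = 56, 112 and 168 days.

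**Assumptions.** First m = 7 days low by L mL, then level; no missing days; true linear decline R of 100-200 mL/year.

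**1. Least-squares slope on all daily values.** The bias per year is 365.25 × 6m(n − m) / [n(n² − 1)] × L.

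- n = 56: 365.25 × 6 × 7 × 49 / (56 × 3135) = 4.28 L
- n = 112: 365.25 × 6 × 7 × 105 / (112 × 12543) = 1.15 L
- n = 168: 365.25 × 6 × 7 × 161 / (168 × 28223) = 0.52 L

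The L that cancels the slope is R divided by the multiplier.

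**2. Last-week mean minus first-week mean.** The bias is L. The true change between the two windows is R(n − 7)/365.25, which is also the L that cancels it.

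| Follow-up | Slope bias, L = 50 mL | L cancelling the slope, R = 100-200 | L cancelling start-to-end change, R = 100-200 |
|---|---|---|---|
| 8 weeks | +214 mL/year | 23-47 mL | 13-27 mL |
| 16 weeks | +57 mL/year | 87-174 mL | 29-57 mL |
| 24 weeks | +26 mL/year | 192-384 mL | 44-88 mL |

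So at 16 weeks an L of 50 mL hides 29-57% of the assumed slope (57/200 to 57/100). At 24 weeks it hides 13-26%.

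**3. Other learning shapes.** A total gain G that closes linearly over 7 days gives slope multipliers of 2.55, 0.67 and 0.30. An exponential approach with a 7-day time constant gives 3.94, 1.15 and 0.53. Over all three shapes, the gain needed to cancel the slope is 23-79 mL at 8 weeks, 87-300 mL at 16 and 187-664 mL at 24. For the start-to-end change it is 13-47, 29-101 and 44-154 mL.

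**4. Effect of leaving early days out.** If learning is complete by day 7, dropping seven days removes the slope bias. For the exponential shape, the multiplier falls as follows:

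- 8 weeks: from 3.94 to 1.80 (7 days dropped) or 0.85 (14 days)
- 16 weeks: from 1.15 to 0.48 or 0.20
- 24 weeks: from 0.53 to 0.21 or 0.09

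So 40-46% remains after dropping 7 days and 16-21% after 14.

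**5. Precision.** With independent daily errors, the slope standard error grows by about (n/(n − k))^1.5 when k days are dropped. For k = 7: (112/105)^1.5 = 1.10 and (56/49)^1.5 = 1.22. For k = 14: (112/98)^1.5 = 1.22 and (56/42)^1.5 = 1.54.

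**The case against.** A reader might infer that a modest first-week gain can cancel or reverse a true decline anywhere in the 8-24 week range. The arithmetic does not support that. For a slope on daily data it holds only near 8 weeks; at the nominal 16 weeks and beyond the slope is attenuated. Cancellation by a moderate gain at 16 weeks needs a start-to-end estimator, and the available text does not specify one for the trend.

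A reader might also infer that the EWMA screen must fail on a low early run. That cannot be said. The SAP cites an unpublished document whose title concerns cold starts in FVC outlier detection, and its content cannot be seen.

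Nor are patients untrained. They are instructed, their understanding is checked, it is an entry criterion, and help with correct use is available on request (Protocol 6.2.3). Flow chart 2 even marks patient-measured FVC at the baseline visit, which needs reconciling with sending the device afterwards. All this may shrink a learning effect. It neither measures nor excludes one.

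Three further points stand. The documents contain no evidence of a practice gain, and effort that wanes with daily testing would bias the trend the other way. The study is a descriptive pilot without hypotheses, so no error rate or power is affected. Per-patient scatter plots (SAP 5.3) could reveal a marked early rise. But plots do not show how far the cohort trend depends on the early days.

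**Conclusion.** The gap is real and moderate in weight: every day from the first home reading feeds an uncontrolled primary trend, and no planned summary shows what happens without the early days. The direction is clear if early readings are low; the size is unknown. It rests on the assumed L, the assumed decline of 100-200 mL/year, near-daily recording and an estimator that cannot be seen. Under those assumptions the risk is serious for patients followed for about 8 weeks, or if the trend is reported as a start-to-end change. For a daily-data slope at 16-24 weeks it is a partial masking of decline. The consequence is a misleading description, not an invalid test. This is a cheap improvement, not a flaw that undermines the study.

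**What to change.** In SAP 5.3:

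- Keep the all-data trend as it is.
- Beside it, present the same summary with the first 7 days excluded, counted from each patient's first home reading, and again with the first 14 days excluded, because slower learning survives a 7-day cut.
- Tabulate for each patient the mean of days 1-7 against days 8-14. True decline over that one-week gap is only about 2-4 mL at the assumed rates (100 to 200 × 7/365.25), so a clear rise would point to practice.
- Where the versions differ, report both, and do not describe the cohort as stable or improving on the all-data version alone.
- Label the cut-offs post hoc if the data have been seen. The SAP is written in the past tense and already counts 20 treated patients.

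All readings stay in the listings and plots, and no patient procedure changes. The cost is a few table rows and a less precise second version: slope standard error about 10% larger at 16 weeks and 22% at 8 weeks for the 7-day cut, and 22% and 54% for the 14-day cut. If there is no learning, the versions should agree apart from noise and the conclusion is stronger for it. The comparison does not address waning effort later in follow-up.

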3.2 Discussion of study design

This is an open-label, single group observational study. There is no control group.

Patients will follow their usual care programme throughout the study. The study observation period (16 ± 8 weeks) is approximately equal to the interval between clinic visits in the usual care of IPF.

This design will enable assessment of longitudinal trends in FVC and PROMs in a cohort of patients with IPF undergoing usual care.

Patients enrolled in the study will capture information on relevant health outcomes related to IPF on a regular basis (daily for some parameters) using the patientMpower app. Patients will also measure FVC at home once per day using the Spirobank Smart spirometer. The patient measured FVC and other spirometry data will be captured automatically by the patientMpower app. These data will form the patient-reported outcome database.

Clinical assessments (e.g. FVC, dyspnoea) in the same cohort of patients will be assessed at the beginning and end of the study. PROMs will also be recorded at the clinic at the beginning and end of the study. This design allows comparison of patient-reported data and their longitudinal trends with clinic-reported data in a cohort of patients with IPF. The correlation between the two types of data and the value of patient measurements in predicting health outcomes can be assessed and quantified.

This design will also allow evaluation of the utility and acceptability of the patientMpower app in a patient population managed by centres with expertise in the diagnosis and management of IPF. This will be assessed from both the patient and healthcare professional perspectives.

The patientMpower app will include key questions derived from a PROM developed specifically for patients with IPF [5] and will help to evaluate the utility of an electronic health diary in capturing PROM data in IPF patients.

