STUDY OBJECTIVES	 Characterise longitudinal trends of patient-reported Forced Vital Capacity (FVC) and outcome measures in patients with idiopathic pulmonary fibrosis (IPF). Determine the correlation between patient-reported FVC and outcome measures with clinic-observed measurements. Assess if longitudinal trends in patient-reported FVC predict clinical outcomes. Characterise the acceptability and utility of the patientMpower app from patient and healthcare professional perspectives.
METHODOLOGY	Prospective, open-label, single-arm observational study. Usual care for all patients throughout study.
NUMBER OF SUBJECTS	Total randomised: target = 25

	Actual intention-to-treat: 21. Treated dataset: 20
DIAGNOSIS	Confirmed diagnosis of IPF
MAIN CRITERIA FOR INCLUSION	Age ≥18 years, daily access to smartphone or tablet device, email address, demonstrated understanding of use of patientMpower app and home spirometry, written informed consent
TEST PRODUCT	patientMpower intervention (defined as patientMpower app + home spirometer) used daily + usual care
COMPARATOR PRODUCT	None
DURATION OF OBSERVATION	Sixteen ± eight weeks (corresponding to interval between usual care visits)
END OF STUDY DEFINITION	Date of first usual care visit after baseline visit (typically at sixteen ± eight weeks)
PRIMARY ENDPOINTS	Trend of patient-measured FVC over time. Degree of correlation between patient- measured FVC with clinic- observed measures
SECONDARY ENDPOINTS	Trends of patient-reported outcomes over time. Degree of correlation between patient- reported outcomes with clinic-observed measures. Patient and healthcare professional perspectives on preference for and difficulty using the app and helpfulness in managing IPF. Impact of app on patient self- management of IPF and daily living.
INTERIM ANALYSIS	Analysis of data up to 18 October 2019 to prepare abstract for American Thoracic Society 2020
STATISTICAL METHODS	Descriptive statistics tables prepared for all endpoints

FLOW CHARTS

Flow chart 2: Assessments during observation period

	Baseline (clinic visit)	Install app & pair spirometer	*Daily (patient - reported)	16 (±8) weeks End study (clinic visit) ¹
	day 0	day 0-2	daily	week 16
				(approx.)
Informed consent	Х			
Start of study	Х			
Spirometry, assess dyspnoea	Х			X
Demographic data (include IPF history & medicines history ³)	Х			
Patient training &	Х			
encouragement				
Installation of		Х		
patientMpower app & pair				
spirometer				

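### SAP 5.3 summarises the paired home and clinic FVC values only by a Pearson r at each visit; the mean difference and limits of agreement should be reported from the same pairs

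*SAP*

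**What the plan says.** The SAP synopsis lists as a primary endpoint: "Degree of correlation between patient- measured FVC with clinic- observed measures". SAP 5.3 implements it. After outlier removal, home readings are averaged over the seven days after the baseline clinic FVC and the seven days before the end-of-study clinic FVC. Then: "For both baseline and end-of-study, the correlation between in-clinic FVC and patient-recorded FVC was calculated" by resampling and "calculating the usual Pearson correlation coefficient", 1000 times at each visit. On who contributes: "Patients without a single spirometry value in either 7 day window were excluded". The per-patient display covers home data: "Scatter plots of patient-recorded FVC versus time were prepared for each patient". Clinic values on those plots are not mentioned.

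The protocol describes a broader purpose. Section 5.1.2 says the primary endpoint data will be assessed by change in home FVC and by comparing it with clinic FVC measured at the start and finish of the study. Section 3.2 says: "This design allows comparison of patient-reported data and their longitudinal trends with clinic-reported data". Neither section names a statistic for that comparison, though 3.2 also speaks of correlation.

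Two places might hold more. The synopsis promises: "Descriptive statistics tables prepared for all endpoints". SAP 5.3 also refers the reader to Appendix 1 for its list of comparisons and tests. Section 7.1 gives that appendix only as a separate file, and its contents are not in the text reviewed.

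**The concern.** Pearson r measures how closely points lie to some straight line, not to the line where home equals clinic. If home readings sit a fixed amount or a fixed percentage away from clinic readings, r is the same as if they agreed. Patients also differ much more in lung volume than in measurement error, so r across patients tends to be high even when individual home and clinic values differ appreciably.

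The documents give a reason to look for an offset, although they do not show that one exists. Home FVC is a single manoeuvre per day (Protocol 4.1.1 and 6.2.3), and SAP 5.3 anticipates blows that lack force or are broken by coughing. The outlier screen compares each value with the patient's own moving average, so it would not be expected to remove a consistent home-versus-clinic difference.

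At stake is how the result is read. A reader who sees r of 0.95 or so may take it that home and clinic FVC agree. The pairs already formed could answer that directly in litres, and r cannot.

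**Working it through.** The documents contain no FVC result, SD or precision target, so there is no plan figure to reproduce. Pair counts come from the SAP; all SDs are assumptions, shown as ranges.

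**Pairs.** The treated dataset is 20 (SAP synopsis). Two patients had no end-of-study clinic visit (SAP 1.3). That leaves at most 20 pairs at baseline and 20 − 2 = 18 at end of study, or 19 if one of the two was the consented patient outside the treated dataset. Empty 7-day windows reduce these counts.

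**Constant or proportional offset.** For home H, clinic C and any b > 0, corr(a + bH, C) = corr(H, C). With the same readings kept, home values 0.3 L low (a = −0.3) or 10% low (b = 0.9) leave r exactly unchanged. In one simulated set of 20 pairs, r was 0.8643 in all four of these cases:

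- no shift: mean difference −0.01 L
- shift of −0.3 L: mean difference −0.31 L
- shift of −0.5 L: mean difference −0.51 L
- scaling by 0.8: mean difference −0.57 L

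**Offset that varies between patients.** Assumed mid-range SDs: between patients 0.7 L; true change 0.15 L; error 0.15 L per clinic value and per home reading; each home value the mean of 7 independent readings.

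- True variance at end of study: T = 0.7² + 0.15² = 0.5125
- Home error variance: vh = 0.15²/7 = 0.0032
- Clinic error variance: vc = 0.15² = 0.0225
- Patient-specific offset SD: so
- r = T / √[(T + vh + so²)(T + vc)]
- SD of difference = √(vh + vc + so²); limits of agreement = mean ± 1.96 × SD

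For so = 0: r = 0.5125/√(0.5157 × 0.5350) = 0.976 and SD = √0.0257 = 0.160 L. For so = 0.30: r = 0.5125/√(0.6057 × 0.5350) = 0.900 and SD = √0.1157 = 0.340 L.

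| Offset SD (L) | r | Limits of agreement (L, around the mean) |
|---|---|---|
| 0 | 0.976 | ±0.31 |
| 0.10 | 0.966 | ±0.37 |
| 0.20 | 0.940 | ±0.50 |
| 0.30 | 0.900 | ±0.67 |

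The limits roughly double while r stays at 0.90 or above.

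**Precision of the added statistics at n = 18.** The 95% CI half-width is t(17) × SD/√18 = 0.497 × SD for the mean difference, and t(17) × SD × √(1/18 + 1.96²/34) = 0.866 × SD for each limit. With clinic and home error SDs of 0.10 to 0.20 L, 7 readings per window and no patient-varying offset, SD runs from 0.107 to 0.214 L:

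- mean difference: ±0.05 to ±0.11 L
- each limit: ±0.09 to ±0.19 L

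If every window held only one reading, SD would be 0.141 to 0.283 L and the mean difference ±0.07 to ±0.14 L. With an offset SD of 0.30 L (SD 0.340 L), the figures are 0.497 × 0.340 = ±0.17 L and 0.866 × 0.340 = ±0.29 L.

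**Change against change.** If true changes are shared, r_change = sc²/√[(sc² + 2vh)(sc² + 2vc)], where sc is the true-change SD. Mid-range: 0.0225/√(0.0289 × 0.0675) = 0.51, Fisher 95% CI at n = 18 of 0.06 to 0.79. The 16-point grid takes between-patient SD 0.6 or 0.8 L, and true-change, clinic-error and home-error SDs each 0.10 or 0.20 L. Over it, r_change runs from 0.23 to 0.79.

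To see whether this adds much, compare shared with wholly unrelated true changes. The 95% CIs for end-of-study r overlap at 14 of 16 points. The CIs for r_change (shared value against 0) overlap at the same 14. The planned analysis also gives a baseline r. In simulation of the mid-range case, the fall in r from baseline to end of study separates the two situations with an area under the ROC curve of about 0.92, against about 0.94 for r_change.

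**The case against.** The strongest reply is that the SAP does what its endpoint says. The endpoint is correlation, no hypothesis is tested, the study is a small pilot of arbitrary size, and no claim is planned that home can replace clinic spirometry. All of this stands, so Pearson r is not an error. It does not make r a full answer to Protocol 5.1.2, which promises a comparison with clinic FVC at both ends of the study.

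A second reply is that Appendix 1 or the descriptive tables may already cover this. The appendix may, so the point applies to SAP 5.3 and the text available. Descriptive tables may show a group mean offset, but they would not by themselves give limits of agreement.

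Third, every SD above is assumed, and a uniform offset leaves the direction of each patient's home trend intact. Both are true. The invariance of r to such an offset is algebra, however, and needs no assumed SD.

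A reader might go further and infer that, because two cross-sectional r values never pair a patient's home change with that patient's clinic change, the planned analysis cannot detect loss of tracking. That is not supported. Loss of tracking would tend to lower r at end of study relative to baseline, and under the assumed model that fall discriminates almost as well as change against change. Wholly unrelated true changes are also an extreme case, since both instruments measure the same lungs.

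**Conclusion.** The point holds as an improvement to SAP 5.3, not as an error in it. In the text available, the home and clinic pairs are reduced to one r per visit. That r is blind to a constant or proportional offset and only weakly sensitive to one that varies between patients (0.976 to 0.900 while the limits go from ±0.31 to ±0.67 L, under assumed mid-range SDs). The mean difference and limits of agreement supply what is missing and would be usefully precise at about 18 pairs, less so if windows are sparse or offsets vary widely between patients.

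The conclusion does not extend to saying that home readings are low, that interchangeability was claimed, or that tracking goes unexamined. Confidence is medium because Appendix 1 has not been seen.

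**What to change.** Keep the Pearson r. In SAP 5.3, add for each visit, from the same pairs:

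- the number of pairs, stating whether an empty window removes a patient from that visit only or from both
- the mean home-minus-clinic FVC difference with a 95% CI
- the Bland-Altman 95% limits of agreement, each with its 95% CI
- a sentence saying that a high r is not to be read as agreement

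If Appendix 1 already lists these, cite it in 5.3. If not, label them post hoc, because the SAP was written after data collection.

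Optional and exploratory: mark the clinic values on each patient's scatter plot, and report home change against clinic change, noting that it is imprecise and attenuated by measurement error.

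The cost is some SAP wording and a small table per visit from data already held. No new measurements or patients are needed. The drawback is that the additions will probably have to be presented as post hoc.
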